### **Action Taken Regarding Investigational Product**

The action taken must be described by choosing among:

- Dose not changed: No action is taken regarding the study medication.

CONFIDENTIAL

- 
- Study medication permanently withdrawn: Subject is permanently withdrawn from the study.
  - Study medication temporarily withdrawn: Study drug is temporarily withdrawn.
  - Not applicable: Other situations (e.g., AE started after the last study medication administration).

### **Outcome**

Each AE must be rated by choosing among:

- Recovered/resolved.
- Recovered/resolved with sequelae.
- Not recovered/not resolved.
- Fatal.
- Recovering/resolving.
- Unknown.

#### **8.7.1.4.1.2 Recording Adverse Events**

AEs will be recorded from the signature of ICF until the final Follow-up visit. In case an AE is ongoing at the Follow-up visit, it will be followed up until resolution or until stabilization, according to the investigator's medical judgement.

It is the responsibility of the investigator to collect all AEs (both serious and nonserious) derived by spontaneous, unsolicited reports of subjects, by observation and by routine open questioning (such as "How do you feel?").

Any adverse or unusual event occurring during or after the clinical study (until the Follow-up visit or the moment of rollover to the Follow-up study GLPG0634-CL-205), whether observed by the investigator or investigational staff, or spontaneously reported by the subjects will be recorded in the eCRF.

#### **8.7.1.4.1.3 Managing Serious Adverse Events**

Subjects experiencing an SAE or an emergency situation will be examined by a physician as soon as possible. The physician in attendance will do whatever is medically needed for the safety and well-being of the subject. The subject will remain under observation as long as medically indicated. Appropriate laboratory studies will be conducted until all parameters return to normal or are otherwise explained or stable. The subject will be followed until the SAE resolves or until the subject is medically stabilized.

#### **8.7.1.4.1.4 Reporting Serious Adverse Events to [REDACTED]**

All SAEs, whether or not deemed study medication-related, must be recorded in the eCRF and SAE form and reported by the investigator to [REDACTED]

[REDACTED] (Belgium) within 24 hours by facsimile. Other means of transmission can be decided where facsimile is not possible. The SAE should include a clearly written narrative describing signs, symptoms, and treatment of the event, diagnostic procedures, as well as any relevant laboratory data and any sequelae.

Follow-up and outcomes should be reported for all subjects that experience an SAE. It is critical that the information provided on the [REDACTED] SAE form matches the information recorded on the eCRF for the same event. In addition, the same information is to be recorded in the source documents.

Copies of additional laboratory tests, consultation reports, post-mortem reports, hospital case reports, autopsy reports, and other documents should be sent when requested and applicable. Follow-up reports relative to the subject's subsequent course must be submitted to [REDACTED] until the event has subsided or, in case of permanent impairment, until the condition stabilizes.

The contact persons are:

| Name and Title                           | Telephone no. | Fax no.    | E-mail     |
|--|---------------|------------|------------|
| [REDACTED]                               | [REDACTED]    | [REDACTED] | [REDACTED] |
| [REDACTED]                               | [REDACTED]    | [REDACTED] | [REDACTED] |
| [REDACTED]
Medical Safety
Officer* | [REDACTED]    | [REDACTED] | [REDACTED] |

\* The Medical Safety Officer at Galapagos is the sponsor liaison for [REDACTED] assessment of SAEs.

#### **8.7.1.4.1.5 Pregnancy**

All initial reports of pregnancy in a subject and pregnancies in partners of male subjects included in the study must be reported to [REDACTED] by the investigator within 24 hours of knowledge of the event, using a pregnancy form. Any subject who becomes pregnant during the study must be promptly withdrawn from the study (not applicable if subjects are male). Spontaneous abortion is considered an SAE and will be reported as such.

The investigator will contact the subject at the expected time of delivery for follow-up on the pregnancy outcome. Abnormal pregnancy outcomes are considered SAEs and must be reported using the SAE Form.

#### **8.7.1.4.1.6 Reporting Serious Adverse Events to Competent Authorities/ Ethics Committees**

[REDACTED] assumes responsibility for appropriate reporting of AEs to the regulatory authorities. [REDACTED] will also report to the investigator(s) all SAEs that are unlisted (unexpected) and associated with the use of the study medication. The investigator(s) (or [REDACTED] where required) must report these events to the appropriate IEC/IRB that approved the protocol unless otherwise required and documented by the IEC/IRB.

AE reporting, including suspected unexpected serious adverse reactions, will be carried out in accordance with applicable local regulations.

After termination of the clinical study (last subject last contact in the study), any unexpected safety issue that changes the risks benefit analysis and is likely to have an impact on the

CONFIDENTIAL

subjects who have participated in it, will be reported by the sponsor [REDACTED] as soon as possible to the competent authority(ies) concerned together with proposed actions.

#### **8.7.1.4.2 Clinical Laboratory Evaluation**

The hematology and clinical chemistry laboratory analyses will be performed at a central laboratory ([REDACTED]). Reference ranges will be supplied by the central laboratory and used by the investigator to assess the laboratory data for clinical significance and pathological changes.

The total amount of blood to be taken during the study will not exceed 600 mL.

The following laboratory safety tests will be performed at every visit:

##### **Hematology**

Hemoglobin, hematocrit, WBC count (total and differential), RBC count, differential lymphocyte count (by flow cytometry: CD3, CD19, CD4, CD8, CD3-/CD16+, and CD56+), platelet count, activated partial thromboplastin time, and prothrombin time.

##### **Clinical Chemistry**

Creatinine, blood urea nitrogen (BUN), AST, ALT, gamma glutamyltransferase (GGT), alkaline phosphatase, total bilirubin, amylase, lipase, albumin, total protein, sodium, potassium, chloride, glucose, uric acid, total cholesterol, HDL and LDL, triglycerides, calcium, phosphorus, and CRP.

Serum pregnancy test for females of childbearing potential at Screening and Week 24 only/EDV only.

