## **6.2 Background on GLPG0634**

Janus kinases are intracellular cytoplasmic tyrosine kinases (TYKs) that transduce cytokine signaling from membrane receptors to the nucleus of cells. JAK inhibitors block the signaling of various cytokines, growth factors and hormones, including the pro-inflammatory cytokine interleukin (IL)-6. Four different types of JAKs are known which (co-)interact with different sets of membrane receptors: JAK1, JAK2, JAK3 and TYK2. Inhibition of JAKs is a promising therapeutic option for a range of inflammatory conditions including RA and Crohn's disease (CD).

GLPG0634 is a potent and selective inhibitor of JAK1. The compound is currently in phase II development for RA and CD and has shown good preliminary efficacy in RA patients. No typical JAK2 side effects such as anemia were observed in clinical studies. The anticipated therapeutic daily dose range is 50 to 200 mg.

GLPG0634 is metabolized to form one major active metabolite, G254445. Though the potency of this metabolite is lower than the parent molecule, the overall exposure and peak plasma concentration in humans is higher. As a consequence, dedicated pharmacology and toxicology studies have been performed with G254445. Results from pharmacodynamics (PD) testing in healthy volunteers suggest that the clinical activity of GLPG0634 could result from the combination of the parent molecule and the metabolite.

More information on the study drug along with references to support the cited data are presented in the Investigator's Brochure (IB). A summary is provided hereafter.

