#### **8.6.2.5 Week 12 (Visit 7)**

The Week 12 visit (Visit 7) will take place on Day 85 ± 2 calendar days relative to the start of study medication intake.

- Any remaining study medication as well as empty study medication containers will be returned to the investigator and an accountability check will be performed.
- Any AEs that have occurred since signing the ICF will be documented, and any changes in concomitant medication will be reported.
- Vital signs will be measured.
- A 12-lead ECG will be performed.
- A physical examination will be performed.
- The subject diary card will be collected, a summary will be recorded in the eCRF, and a new subject diary card will be dispensed.
- Blood samples for measurement of PK and PD parameters will be collected.
- Serum CRP will be measured.
- SJC66 and TJC68 evaluations will be performed.
- Physician's and Patient's Global Assessments of Disease Activity will be completed.
- The subject will complete the HAQ-DI.
- The subject will complete the FACIT fatigue scale and the SF-36 questionnaire.
- Hematology, clinical chemistry, and urinalysis (dipstick and microscopy) tests will be performed on samples collected at this visit. A urine pregnancy test will be performed on females of childbearing potential.

CONFIDENTIAL

At visit 7, subjects on placebo who have not achieved a 20% improvement in SJC66 and TJC68 will be re-randomized (automatically via IXRS) to treatment to receive GLPG0634 100 mg q.d. or 50 mg b.i.d. doses in a blinded fashion, subjects on 50 mg q.d. who have not achieved a 20% improvement in SJC66 and TJC68 will be assigned to 100 mg q.d. and subjects on 25 mg b.i.d. who have not achieved a 20% improvement in SJC66 and TJC68 will be assigned to 50 mg b.i.d. All will continue the study until Week 24. Subjects in the other groups will maintain their randomized treatment until Week 24.

When all of these procedures have been performed, the study medication will be dispensed according to the information provided using IXRS and the date of the next visit confirmed.

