##### **8.7.1 Efficacy, Pharmacokinetics, Pharmacodynamics and Safety Measurements Assessed and Flow Chart**

###### **8.7.1.1 Efficacy Assessments**

###### **8.7.1.1.1 Evaluation of Disease Activity**

Efficacy assessments will be carried out at Screening (joint counts and Patient's Global Assessment of Disease Activity only); Baseline (Day -1); at Weeks 1, 2, 4, 8, 12, 16, 20, and 24; and at the EDV (if applicable).

Each of 68 joints will be evaluated for tenderness, and each of 66 joints will be evaluated for swelling (Appendix 13.2).

A joint assessor with adequate training and experience in performing joint assessments will be designated at each study site to perform all joint assessments. The joint assessor should preferably be a rheumatologist, however, if a rheumatologist is not available, it should be a health care worker with at least one year's experience in performing joint assessments. The assessor should remain the same throughout the study per subject, as much as possible. It is required that the designated joint assessor identify an appropriate back-up assessor to provide coverage if the designated joint assessor is absent.

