#### **8.8.1.3 Efficacy Variables**

##### **Definition of Primary Efficacy Endpoint - ACR20 at Week 12**

The primary endpoint is the percentage of subjects achieving an ACR20 response at Week 12. Other time points will be regarded as secondary endpoints.

The ACR response is a measurement of improvement in multiple disease assessment criteria. The ACR20 response is defined as:

≥20% improvement from Baseline in SJC66 (66 joints) and TJC68 (68 joints)

AND

CONFIDENTIAL

≥20% improvement from Baseline in at least 3 of the following 5 assessments

- Pain (VAS) in cm (from HAQ-DI).
- Patient's Global Assessment of Disease Activity (VAS) in cm.
- Physician's Global Assessment of Disease Activity (VAS) in cm.
- Patient's Assessment of Physical Function as measured by HAQ-DI.
- CRP in mg/dL or mg/L.

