**12.2. LABORATORY SAFETY****12.2.1. Laboratory Units**

The statistical analysis will only present results in Standard International (SI) units. Other units will not be presented.

Lab tests with only a very low sample size ( $N < 3$  in the study total column) will not be presented in the tables, but only in the listings. Lab tests that are not part of the planned test panels according to the protocol will only be listed.

Endocrine tests will only be presented for male subjects. If any results would be available for females (not planned in the protocol), then these will be left out of the tables but still presented in the listings.

Urinalysis tests will be presented as part of the descriptive statistics and/or shift tables.

The serum CRP will not be presented in this section (is considered an efficacy parameter).

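### The protocol does not keep post-baseline CRP, an ACR20 component, from the site staff who score the joint counts and the physician's global assessment, which leaves an avoidable risk to blinding

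*Protocol*

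**What the plan says.** Protocol section 8.7.1.4.2 introduces the central-laboratory panel with "The following laboratory safety tests will be performed at every visit". The reference ranges are to be "used by the investigator to assess the laboratory data for clinical significance and pathological changes". The Clinical Chemistry list closes with "total cholesterol, HDL and LDL, triglycerides, calcium, phosphorus, and CRP". CRP is also named as a procedure at each visit; the Week 12 entry in section 8.6.2.5 reads "Serum CRP will be measured".

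CRP is an efficacy variable too. The ACR20 definition in section 8.8.1.3 includes "CRP in mg/dL or mg/L" among the five items of which three must improve, and CRP enters DAS28(CRP), SDAI and ACR/EULAR remission. SAP section 12.2.1 says "The serum CRP will not be presented in this section (is considered an efficacy parameter", and SAP section 8.8.1 excludes CRP and hsCRP from the laboratory safety analysis.

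On who rates, section 8.7.1.1.1 requires a trained joint assessor who "will be designated at each study site to perform all joint assessments". Section 8.7.1.1.3 requires only that the physician's global be independent of the patient's. Section 8.5.7 (Blinding) covers treatment assignment and does not mention laboratory results.

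**The concern.** As written, CRP follows the same route as ALT or creatinine: central laboratory, then the investigator. Yet the plan makes no stated safety use of it after baseline. The site use it names is Screening eligibility.

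ACR20 requires at least 20% improvement in both SJC66 and TJC68, which are scored at the site, as is the physician's global. If a rater knows that a subject's CRP has fallen and takes that as a sign of active drug, borderline joint findings may be scored more favourably. The reverse may happen when CRP has not moved. All six primary comparisons are against the one placebo arm, so such a bias would favour the drug in each of them. The same joint counts also decide at Week 12 which placebo and lowest-dose subjects change treatment, so biased scoring could alter the treatment received as well.

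**Working it through.** **Step 1. Does the text expose CRP to the raters?** Setting the sections side by side:
- Protocol 8.7.1.4.2: CRP is in the every-visit panel that the investigator assesses.
- Protocol 8.6.2.1 to 8.6.2.4: serum CRP is measured at Weeks 1, 2, 4 and 8. The test is central, so a visit's own result is probably not known when that visit is scored, but these four could be known by Week 12.
- Protocol 8.5.7, 8.7.1.1.1 and 8.7.1.1.3: none masks laboratory data or separates the raters from it.
- Protocol 8.3.4: none of the listed individual stopping criteria uses CRP.

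Release of CRP to sites is therefore the natural reading, but it is inferred. No sentence states it, and none contradicts it.

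**Step 2. Would CRP be informative?** Protocol section 6.2 says "JAK inhibitors block the signaling of various cytokines, growth factors and hormones, including the pro-inflammatory cytokine interleukin (IL)-6". That is a statement about the class. The step to a lower CRP on GLPG0634 is an inference, supported indirectly by SAP Table 14.2.1.8.5, which tabulates CRP normalizations.

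For a standardized active–placebo difference d in CRP change (assumed; normal distributions with equal variance), AUC = Φ(d/√2) and balanced accuracy = Φ(d/2):
- d = 0.25: AUC 0.57, balanced accuracy 55%
- d = 0.5: 0.64, 60%
- d = 1.0: 0.76, 69%

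Any clue is probabilistic.

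**Step 3. Reproduce the plan's power.** Inputs from protocol section 8.8.2: n = 85 per arm, α = 0.05/6 = 0.00833. The two-sided critical value is 2.638. With p̄ = (p₀+p₁)/2,

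SE₀ = √[2p̄(1−p̄)/n], SE₁ = √{[p₀(1−p₀)+p₁(1−p₁)]/n}, power = Φ[(p₁−p₀−2.638·SE₀)/SE₁].

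Results: 20% vs 48%, 89.8%; 40% vs 70%, 91.3%; 20% vs 45%, 80.9%; 40% vs 66%, 78.4%. These agree with the stated 90% and 80% to within 2 points. One-sided α gives 93.7%, 94.7%, 87.0% and 85.0%, which does not match, so α is taken as two-sided.

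**Step 4. Illustrate what a scoring bias would do.** Assume no true effect and that bias adds b points to ACR20 in an active arm, so p₁ = p₀ + b. The same formula gives the chance of a significant result favouring drug. Example with p₀ = 30% and b = 5 points: SE₀ = 0.07185, SE₁ = 0.07174, (0.05 − 2.638 × 0.07185)/0.07174 = −1.945, and Φ = 2.6%.

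| Assumed shift b | Placebo 20% | Placebo 30% | Placebo 40% |
|---|---|---|---|
| 0 | 0.42% | 0.42% | 0.42% |
| 3 points | 1.5% | 1.3% | 1.3% |
| 5 points | 3.1% | 2.6% | 2.4% |
| 10 points | 12.7% | 10.1% | 9.1% |

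The comparator is 0.42%, half of 0.83%, because only errors in the drug's favour are counted. The shifts have no source in the documents.

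**The case against.** The strongest reply is that the key fact is not written down. Serum CRP has its own row in the flow chart (protocol section 8.7.1.5), separate from clinical laboratory tests, and the SAP distinguishes regular from high-sensitive CRP. A laboratory manual outside these documents may already restrict reporting. This stands as a limit. It does not remove the point, because the protocol as written has CRP in the panel the investigator assesses.

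Three stronger readings are tempting, and the documents do not support them.

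- *A reader might infer that CRP reveals treatment.* Six of the seven arms are active, so always guessing active is right 6/7 = 85.7% of the time. Under the assumptions of Step 2, adding CRP leaves the best overall guess at 85.7% for d = 0.25 or 0.5 and raises it only to 86.2% for d = 1.0. CRP also tracks disease activity, so a fall often accompanies visible joint improvement. CRP can still shift a rater's belief about individual subjects, as the AUC values show, and that is all the point needs.
- *A reader might infer that every subjective ACR20 item is affected.* Pain, the patient's global and HAQ-DI are completed by the subject, and nothing shows that subjects see results. Direct exposure is limited to SJC66, TJC68 and the physician's global. The last is one of five items of which three suffice. That the joint assessor reads laboratory reports is itself an assumption.
- *A reader might take the table in Step 4 as the trial's error rate.* It shows what any bias of that size would do, not that CRP visibility would cause one.

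It is also fair to say that masking CRP is a partial remedy. Protocol section 8.8.1.8 names neutrophils and LDL as parameters that treatment might alter, and section 8.5.8 leaves local methotrexate testing in place. Nor does the absence of a CRP stopping rule prove that sites have no safety use for it, since it is listed under safety tests and infections are monitored closely. Clinical access therefore needs to be provided for.

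**Conclusion.** The point holds as a gap in the protection of the blind. The plan places an efficacy readout in the panel the investigator assesses and has no provision keeping it from the people who score both mandatory ACR20 joint counts. It rests on two inferences: that post-baseline CRP reaches sites with the rest of the panel, and that CRP tends to fall on active drug. Both are reasonable on the text; neither is stated.

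The size of any bias cannot be estimated from the documents. The Step 4 figures depend wholly on assumed shifts and should be quoted only with that label and against the 0.42% null. No sample-size figure is affected. The change is cheap and worth making, but the documents do not show that the blind fails.

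**What to change.** Adopt one or both of the following:
1. In protocol sections 8.7.1.4.2 and 8.5.7, state that post-baseline central-laboratory CRP and hsCRP are left off the routine site report and sent to the efficacy database only.
2. In section 8.7.1.1, state that the joint assessor, who is already a designated person, and the physician scoring the global assessment do not view post-baseline CRP before scoring.

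Screening CRP stays available for eligibility. Whether and how a site may obtain CRP for clinical reasons is for the sponsor's clinicians to define. If a laboratory manual already masks CRP, one cross-reference in the protocol settles the point.

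The cost is a central-laboratory report setting and a few sentences. Sample size, visits and endpoint are unchanged. The downside is that routine CRP becomes less accessible to sites, and other laboratory changes or local testing may still give clues.

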##### **Hormone tests (for male subjects only)**

Testosterone (total and free), LH, FSH, prolactin, and inhibin B.

##### **Urinalysis**

pH, glucose, ketone bodies, indicators of blood and WBC, and protein (quantitative).

Urine pregnancy test for females of childbearing potential at all visits, excluding Screening and Week 24/EDV.

#### **8.7.1.4.3 Other Laboratory Variables**

##### **Serology**

Hepatitis B and C, HIV 1 and 2, RF and anti-CCP at Screening only.

##### **Other**

TB (QuantIFERON-TB Gold) test at Screening only.

#### **8.7.1.4.4 Vital Signs**

Vital signs (blood pressure, HR and oral temperature) will be recorded as described in the schedule of observations in a standardized manner, i.e. after the subject has rested in the sitting position for 5 minutes.

#### **8.7.1.4.5 Physical Examination**

A physical examination will be performed at times as described in the schedule of observations. Any changes from the Baseline assessment will be recorded. Height and weight will be measured at Screening only.

#### **8.7.1.4.6 Other Safety Assessments**

##### **12-lead ECG**

A resting 12-lead ECG will be performed at times presented in the schedule of observations.

Subjects should rest for at least 5 minutes in the supine position before ECG evaluation.

Parameters to be recorded in the eCRF include: HR, RR, QRS, uncorrected QT, morphology, and rhythm analysis. QTcF will be derived during the statistical analysis. ECGs will be interpreted by the investigator for clinical significance and results will be entered into the eCRF.

##### **Chest X-ray**

A chest X-ray (both anterior-posterior and lateral views) will be taken during the Screening period and reviewed by a qualified radiologist. If chest radiographs have been taken within 12 weeks of the Screening visit (documented evidence is needed) then the chest radiographs do not need to be repeated (as long as they demonstrate no clinically significant abnormality, and no signs or symptoms suggestive of lung disease including current active or latent TB, which would exclude the subject from the study). The results must be entered into the eCRF.

